5. To evaluate the asthma control and health care utilization of subjects as measured by the number of exacerbations (acute worsening of asthma requiring at least 3 days of corticosteroids or a doubling dose of maintenance steroids), Emergency and hospitalization encounters, and patient-reported perceptions of asthma control.
6. To employ machine learning techniques to a robust well characterized cohort with clinical, biological, and digital markers to develop a predictive algorithm aimed at identifying responders to biologics. In addition, we would aim to develop an algorithm that can detect early changes in measured parameters that can predict long-term improvements in asthma control and exacerbations when biologics are initiated. The latter objective will be achieved by focusing on the subgroup of patients initiating biologics for the first time or switching between biologics due to perceived inadequate response.

Endpoints:

Primary Endpoint:

Mean and median number of (daily) doses of ProAir® Digihaler™ and AirDuo® Digihaler™ utilized at baseline, temporal patterns in rescue and controller medication utilization, and within-patient parameter mean, median, and variance per-inhalation to establish baselines.

Secondary Endpoints:

1. Proportion of patients with different rates of adherence.
2. Proportion of Patients achieving non-response, partial-responses, and complete response to biologics.
3. Change in Main Peak Inspiratory volume from baseline up to one year.
4. Change in Mean Inspiratory Time from baseline up to one year.
5. Change in mean peak inspiratory flow (PIF) from baseline up to one year.
6. Change in mean forced expiratory volume in one second (FEV1) from baseline up to one year.

Exploratory Endpoints

7. Number of exacerbations from baseline up to one year.
8. Number of hospitalizations.

9. Number of emergency room visits.
10. Mean Asthma Control Test (ACT) scores.
11. Algorithm that produces a daily asthma exacerbation probability given a set of baseline and current inhalation parameters. A confusion matrix summarizing the algorithm's performance on training dataset and from which performance statistics (accuracy, sensitivity, specificity, etc.) can be computed.

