2 INTRODUCTION

2.1 STUDY RATIONALE & BACKGROUND

Severe asthma affects 10% of the adult population and these patients suffer an increased number of exacerbations and subsequent accelerated decline in lung function. Asthma exacerbations are poorly understood and the ability to predict exacerbations is limited. The factors associated with an increased risk of exacerbations include a prior history of exacerbations, elevated type 2 markers, lower lung function and increased short acting beta agonist (SABA) use. The ability to predict the onset of each isolated exacerbation event and to thus intervene is hampered by a lack of access to real-time information about both SABA use and lung function parameters. The Digihaler™ has demonstrated changes in both PIF and SABA doses surrounding acute asthma events (TEVA, unpublished data). The clinical utility of this information will be tested in future trials that aim to examine the impact of data from the Digihaler™ on clinical decision making. The data from the Digihaler™ coupled with clinical characteristics and biomarkers could be utilized to revolutionize how asthma is monitored and how exacerbations are detected.

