4.2 SCIENTIFIC RATIONALE FOR STUDY DESIGN

We designed an open label, single site study and intend to enroll patients in a sequential manner via screening of the EMR system for patients currently receiving biologics or with a pending approval for biologics for asthma. The open label design was selected as we are interested predominantly in inhalation parameters that are collected without any specific actions from participants, thus decreasing any potential changes in medication utilization. We intend to educate the patients on the use of the inhaler and how it has been prescribed but will make no efforts to intervene to encourage compliance with medication utilization, as we are interested in patient behavior and interaction with the device. The application that collects information about inhaler use will be stored on the patients' smart phone, and therefore they may choose to review the information and make changes in their adherence. We will not require patients to utilize the application and will passively record whether patients report using the app or not. We will design a questionnaire that determines patients' opinions of the app if they are utilizing it. All clinical parameters will be collected from the EMR.

Our main objective is to determine baseline inhalation parameters (e.g., peak inspiratory flow) using sample means. According to one study (<https://www.ncbi.nlm.nih.gov/pmc/articles/PMC5328129/>) the PIF mean was 115 and standard deviation was 15. Assuming a 100 patient sample, the 95% CI of our estimate of the PIF sample mean would be plus or minus 3, e.g., 115 (95% CI 112 – 118), which we deem to be of sufficient power for our analysis (<http://statulator.com/SampleSize/ss1M.html>).

Our secondary objective includes training a machine learning model, and one common measure to evaluate model performance is discrimination, assessed by an area under the ROC curve (AUROC). Again, assuming a 100 patient sample and a 50% event rate, we would have adequate power to conclude that a model with an AUROC performance of >0.65 has confidence intervals that won't cross 0.5 (which would be a model that is no better than chance) (<http://www.biosoft.hacettepe.edu.tr/easyROC/>).

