9.2 SAMPLE SIZE DETERMINATION

Sample size calculations were based on peak inspiratory flow measurements.

Based on population-based estimates of peak inspiratory flow:

<https://www.ncbi.nlm.nih.gov/pmc/articles/PMC5328129/> The mean was 115 and standard deviation was 15. With a 100-patient sample, 95% CI of our estimate of the mean would be plus or minus 3, e.g. 115 (95 CI 112 – 118).

The machine learning model will be performed based on the most common measure to evaluate performance which is discrimination that is assessed by an AUROC. If we have a 100-patient sample and assume a 50% event rate (<http://www.biosoft.hacettepe.edu.tr/easyROC>), we would have adequate power to conclude that a model with an AUROC performance of > 0.65 has confidence intervals that won't cross 0.5 (which would be a model that is no better than chance).

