9.4 STATISTICAL ANALYSES

9.4.1 GENERAL APPROACH

We will perform a retrospective analysis of prospectively enrolled patient data. Following completion of the study's data collection period, data from the Digihaler™ asthma inhalers will be downloaded to secure servers, joined to clinical data from the electronic medical record (including exacerbation event data) and patient questionnaire responses, and analyzed using R statistical analysis software. The University of Michigan Morphomics Analysis Group will collaborate with the TEVA analytics team to produce a rigorous and reproducible research result. An alpha level of 0.05 will be used to determine "statistical significance" with a Bonferroni correction ($\alpha / \# \text{ tests}$) applied to account for multiple testing when appropriate.

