9.4.3 ANALYSIS OF THE SECONDARY ENDPOINT(S)

1. To develop an algorithm that can identify probable imminent exacerbation events using Digihaler™ inhalation parameter measurements, we will compare the performance of several different machine learning regression models. Since we expect our training set to be relatively small with a low event rate, we plan to use the entire inhalation parameter dataset for model training but will employ repeated k-fold cross-validation to reduce variance (over-fitting) and include non-linear features to reduce bias (under-fitting). Examples of features that could be computed and included in this model include but are not limited to: difference between current value and patient-specific 7-day moving average, difference between current value and patient-specific 24-hour moving average, 7-day sample entropy, 24-hour sample entropy, difference in Min-Max over last 24 hours, etc.

A logistic regression model would treat the outcome (exacerbation) as a binary (Yes/No) event. The output of this model would be a daily probability between 0 and 1 that an exacerbation event will occur within a certain period of time. Different models will be fit for different periods of time (e.g., 24, 48, 72 hours) and the performance of each model assessed and compared to others. A recurrent event survival model would treat the exacerbations as discrete events in time. The output of this model would be the predicted time (e.g., in decimal days or hours) until the next event. Other models may include convolutional and/or recurrent neural networks (RNN) with LSTM or GRU architecture with varied numbers of hidden layers.

2. To determine whether and how PIF is associated with FEV1 and FVC, we assess the linearity and strength of the relationship using scatter plots, calculate the paired correlations (Pearson, Kendall, and Spearman), and compute univariate linear regression equations with PIF as the predictor and FEV1 or

FVC as the response. If non-linearity is found, we will determine the appropriate PIF transformation or polynomial term to use in the regression. Regression summary statistics (e.g., R-squared, Mean Absolute Error, Coefficients, and p-values) will be reported.

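### No performance measure for the exacerbation model separates which patient is prone from which day precedes an attack, so the claim to predict imminent events could rest on patient ranking alone

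*Combined protocol and SAP*

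**What the plan says.** - **Hypothesis.** The first secondary hypothesis in 9.1 concerns timing: that exacerbations about to happen can be predicted from Digihaler inhalation measurements.
- **Model.** In 9.4.3 item 1 the logistic model gives "a daily probability between 0 and 1 that an exacerbation event will occur within a certain period of time", fitted separately for windows such as 24, 48 and 72 hours. A recurrent-event survival model and neural networks are alternatives. The section says that the models' performance will be assessed and compared, but names no measure.
- **Inputs.** Endpoint 11 in the Synopsis is an "Algorithm that produces a daily asthma exacerbation probability given a set of baseline and current inhalation parameters". Secondary objective 1 in the Synopsis includes the number of inhaled doses among the predictors. The example features in 9.4.3 are two deviations from the patient's own moving averages, two entropy terms and a 24-hour range; the list is open-ended.
- **Performance output.** Endpoint 11 and the Section 3 table give a confusion matrix on the training dataset, from which accuracy, sensitivity and specificity follow.
- **AUROC.** Section 4.2 says that "one common measure to evaluate model performance is discrimination, assessed by an area under the ROC curve (AUROC". Section 9.2 adds: "If we have a 100-patient sample and assume a 50% event rate", there is adequate power to conclude that "a model with an AUROC performance of > 0.65 has confidence intervals that won't cross 0.5". Neither section ties this to the exacerbation model.
- **Heterogeneity.** Section 2.1 states: "The factors associated with an increased risk of exacerbations include a prior history of exacerbations". It also lists type 2 markers, lower lung function and rescue use.

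**The concern.** Any performance measure computed over all patient-days mixes two abilities: telling frequent exacerbators from stable patients, and telling the days before an attack from other days in the same patient. The hypothesis in 9.1, and the early-detection argument in 2.1, need the second. The plan's own background says that patients differ in risk, and rescue use, one of the risk factors it lists, is what the rescue inhaler records. Dose counts and patient baselines can therefore carry the first kind of information into the model.

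At stake is the main inference from the algorithm. A favourable confusion matrix or AUROC could be reported as detection of imminent attacks when the inhaler had only identified patients whom their exacerbation history already identifies.

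**Working it through.** **1. The plan's own AUROC statement.** Inputs from 9.2: 100 patients and a 50% event rate, so 50 with and 50 without the event; AUROC A = 0.65. Section 9.4.1 sets alpha at 0.05; a two-sided 95% interval is used here. Hanley-McNeil variance:

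Var = [A(1−A) + 49(q1−A²) + 49(q2−A²)] / (50 × 50), with q1 = A/(2−A) = 0.4815 and q2 = 2A²/(1+A) = 0.5121.

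Var = [0.2275 + 49 × 0.0590 + 49 × 0.0896] / 2500 = 0.0030, SE = 0.055, 95% CI 0.543 to 0.757. This excludes 0.5, so the statement reproduces for one outcome per patient.

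**2. Does that setting match the daily model?** No. At an assumed 1 exacerbation per patient-year over 364 days, a 72-hour window marks about 100 × 3 / (100 × 364) = 0.8% of patient-days as positive. Over 0.7 to 2 per year the share is 0.6% to 1.7%. Section 9.4.3 itself expects a low event rate. The calculation in 9.2 therefore describes a patient-level outcome.

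**3. All-days AUROC with no timing signal, exact.** Assume that patient rates follow a gamma distribution with shape k and that events occur at random in time given the rate. Event days then sample patients in proportion to their rate, so the rate behind an event day is Gamma(k+1); behind a non-event day it is approximately Gamma(k). For a score equal to the true rate, AUROC = P[Gamma(k+1) > Gamma(k)]:

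- k = 1: 1 − (1/2)² = 0.75.
- k = 2: 1 − [(1/2)³ + 3 × (1/2)⁴] = 1 − 0.3125 = 0.6875.

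**4. Simulation.** 100 patients × 364 days, 72-hour label, 0.7 to 2 events per patient-year, 200 runs per setting. Ranges are across the four event rates used (0.7, 1, 1.5 and 2):

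| Between-patient rates | All-days AUROC, score = true rate | All-days AUROC, proxy r = 0.5 with log rate | Within-patient AUROC |
|---|---|---|---|
| No heterogeneity | 0.50 | 0.50 | 0.50 |
| Gamma, shape 2 | 0.68–0.69 | 0.59 | 0.50 |
| Gamma, shape 1 | 0.75 | 0.61–0.62 | 0.50 |

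The within-patient column was computed on the proxy plus pure daily noise; a score constant within a patient gives 0.50 by ties. With stronger heterogeneity (shape 0.5) the two all-days figures rise to about 0.82 and 0.63, and the within-patient figure stays at 0.50.

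**5. The same effect in a confusion matrix.** Flag the top fifth of patients on every day. Positive days are rare, so specificity is about 0.80. Sensitivity is the share of all events that falls in the flagged patients. For shape 1 and the true rate this is p(1 − ln p) with p = 0.2: 0.2 × (1 + 1.609) = 0.52. For shape 2 and a proxy correlated 0.5 it is 0.29 (numerical). A flag unrelated to risk gives 0.20. None of these rules contains timing information.

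**6. What the plan has that could separate the two.** Section 9.1 plans a comparison of each patient's baseline usage with usage during or before exacerbations. It tests usage and does not assess the model. A patient-stratified performance measure, a comparator built on known risk factors, and folds grouped by patient appear nowhere.

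**The case against.** The strongest reply is that the plan never commits to a pooled AUROC for this model. A reader might join 9.2 to 9.4.3 and infer that the exacerbation model is judged by a single AUROC pooled over all patients' days, against the 0.5 and 0.65 marks. The documents do not support that. Section 9.4.3 item 1 names neither AUROC nor pooling, endpoint 11 names a confusion matrix, and the 50% event rate fits a patient-level outcome such as the responder model of item 5 at least as well. This reply stands, and the point is confined to what the plan leaves open.

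Other replies stand in part:

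- **Patient-centred features.** No raw level is among the listed examples, and two are explicitly centred on the patient. Baseline parameters could serve only as the reference for such deviations. But the list is open-ended, entropy and range are not centred on the patient's norm, and dose counts are named as predictors. Centring reduces the problem without removing it.
- **Other within-patient elements.** The usage comparison in 9.1, the exclusion of ±14 days around events from baseline (9.4.2) and the recurrent-event model all bear on timing. None measures whether the model gets the timing right, and overall concordance from a survival model can also come from patient ranking.
- **Assumed sizes.** No inhaler variable equals a patient's true rate, and the weak proxy stays below 0.65. This is correct, and the figures are illustrations.
- **Scope.** Predicting exacerbations in general is a legitimate objective, the algorithm is listed as an exploratory endpoint, and 2.1 leaves clinical utility to future trials. That limits the consequences, but 9.1 still states the hypothesis in terms of imminent events.

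**Conclusion.** The point holds as a gap in specification with a real consequence. The unit of prediction is the patient-day, between-patient information may enter the model, and nothing in the plan separates who is prone from when an attack is near. Performance computed over all patient-days could therefore look favourable through patient ranking alone and would not support the hypothesis in 9.1.

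For gamma shape 1 to 2 and no timing signal, the all-days AUROC runs from about 0.59–0.61 (proxy correlated 0.5) to 0.69–0.75 (true rate), against 0.50 within patients. These values depend on heterogeneity that the documents acknowledge but do not quantify, and on events being random in time given the rate. Without heterogeneity the effect vanishes. The figures show what is possible; they do not predict what this study will find. It would go too far to say that the plan prescribes the wrong analysis or that its 0.65 mark will be passed spuriously. Closing the gap is a cheap and worthwhile improvement.

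**What to change.** In 9.4.3 item 1 and endpoint 11, pre-specify for each horizon:

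1. A patient-stratified (within-patient) AUROC or concordance among patients with at least one event, reported next to the all-days measures.
2. A comparator model using only static patient-level risk factors already collected: prior-year exacerbations (8.1.2.1), baseline FEV1 (8.1.2.2 or 8.1.2.5), mean rescue use outside exacerbation windows, and biomarkers when available (8.1.2.2).
3. Cross-validation folds grouped by patient, and intervals from a bootstrap that resamples patients.
4. The rule for claims: prediction of imminent events rests on measure 1; the added value of inhalation parameters rests on the increment over comparator 2.

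Keep the absolute daily-probability model as the algorithm. Conditional logistic regression stratified by patient is at most a supporting analysis: it removes the patient intercepts and so cannot give the daily probability that endpoint 11 requires.

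Cost: SAP wording and some extra analysis, with no new data. Event-free patients do not contribute to the within-patient measure, it will be imprecise if events are few, and reported performance will probably be lower.

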1 PROTOCOL SUMMARY

1.1 SYNOPSIS

Title: Utilizing Advances in Digital Inhaler Technology to Understand Heterogeneous Treatment Responses to Biologics in Severe Asthma

Study Description: This real-world study aims to determine baseline inhalation parameters and patterns of use in patients receiving treatment with TEVA digital inhalers, and to develop predictive models for asthma exacerbations and response to biologics using data collected from these devices.

Objectives:

Primary Objective:
To determine the baseline inhalation parameters and patterns of use of both the maintenance (AirDuo®) Digihaler™ and rescue (ProAir®) Digihaler™ in patients with severe persistent asthma who are being treated with biologics.

Secondary Objectives:

1. To determine the predictive value of inhalation parameters, including peak inspiratory flow (PIF), inspiratory time and volume, and number of inhaled doses on asthma exacerbations in a population of severe asthma patients on biologics.
2. To determine whether inhalation measurements can serve as surrogates of standard expiratory flow measurements. Specifically, to determine the correlation between PIF with FEV1 and identify thresholds for changes in PIF that are associated with a clinically meaningful increases or decreases (10%) in lung function as measured by conventional spirometry (e.g., FEV1).
3. To determine the impact of variable degrees of adherence to maintenance therapy on outcomes to biologics. The Digihaler™ will allow us to collect accurate information on adherence that will be utilized to divide patients into groups and to assess asthma outcomes such as change in mean FEV1, exacerbations, oral steroid reduction, and asthma control (using the asthma control test scores over time) in patients receiving biologic therapies.
4. To determine the impact on inhalation parameters on categorical response to biologics. Response will be categorized as non-response, partial and complete response on the basis of six factors: a 50% reduction in exacerbations, any reduction in maintenance OCS dose, change of at least 10% in FEV1, improvement of 3 points in ACT score, and patient perception of global improvement in asthma.

Exploratory Objectives

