
To determine whether inhalation measurements can serve as surrogates of standard expiratory flow measurements. Specifically, to determine the correlation between PIF with FEV1 and identify thresholds for changes in PIF that are associated with a clinically meaningful increases or decreases (10%) in lung function as measured by conventional spirometry (e.g., FEV1).
	
 • Change in Main Peak Inspiratory volume from baseline up to one year • Change in Mean Inspiratory Time from baseline up to one year • Change in mean peak inspiratory flow (PIF) from baseline up to one year • Change in mean forced expiratory volume in one second (FEV1) from baseline up to one year 
Tests: Correlation coefficients, regression equations, and regression summary statistics (e.g., R-squared,
	
FEV1 is a well-established and accepted measure of lung function in asthma. Changes in FEV1 are noted during acute episodes and clinically meaningful changes have been established. Little is known about the correlation between FEV1 and PIF and whether change in PIF could serve as a surrogate for change in FEV1.

OBJECTIVES	ENDPOINTS	JUSTIFICATION FOR ENDPOINTS
	
mean absolute error) for PIF vs. FEV1, PIF vs. FVC. Identification of change in PIF thresholds (increase and decrease thresholds) that are clinically meaningful.
 
Univariate/multivariate regression statistics between inhalation parameters and asthma outcomes such as asthma control score, number of exacerbations, and number of hospitalizations.
 
Reported confusion matrix for change in PIF versus asthma exacerbations and poor asthma control.
	
Exploratory		

To evaluate the asthma control and health care utilization of subjects as measured by the number of exacerbations (acute worsening of asthma requiring at least 3 days of corticosteroids or a doubling dose of maintenance steroids), Emergency and hospitalization encounters, and patient-reported perceptions of asthma control.
	
 • Number of exacerbations from baseline up to one year • Number of hospitalizations • Number of emergency room visits • Mean Asthma Control Test (ACT) scores 	
Understanding the healthcare utilization and perceptions of asthma control can help researchers better understand how/whether the digihalers are helping the patients achieve better asthma control.

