8.1.2.5 SPIROMETRY

Home spirometry will be performed with the Go Spiro device that is coupled with an avatar that provides coaching and real time feedback about whether the testing has met ATS criteria. Patients will be asked to perform spirometry a *least* three days per week, at least one of which occurs on the weekend. Patients will be asked to make a maximum of three attempts to obtain data. Patients will be encouraged to complete more than three readings per week whenever possible. The spirometry should be obtained at approximately the same time of each day.

The vendor providing central spirometry services will be responsible for assuring that the spirometer used by patients at home meets ATS/ERS criteria and that study staff educating participants on home spirometry have been properly certified to provide this training.

Subjects should be instructed to follow the required restrictions below prior to performing spirometry. If the required restrictions have not been adhered to the visit should be rescheduled to the earliest possible time to maintain the visit windows.

Home Spirometry Testing

An electronic hand-held spirometer will be provided to the subject at the screening visit. Subjects will be trained on how to obtain at home PEF and FEV1 measurements at the screening visit. Training should include explanation of the device functionality and proper use of the PEF meter.

Home PEF measurements will be taken in the morning (prior to taking morning medications) and/or in the evening at bedtime (prior to taking pm medications for asthma) on the days that spirometry is done. FEV1 will be measured at home using accepted ATS/ERS criteria via the use of an avatar guided maneuver. Subjects should perform 3 successive maneuvers while sitting or standing but in the same position at every testing. Adherence to peak flow measurements must be checked by the study coordinator at every in-person visit. A low compliance trigger will be sent to the study site if the subject had completed less than 80% of the expected measurements over a seven-day period.

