9 STATISTICAL CONSIDERATIONS

9.1 STATISTICAL HYPOTHESES

- Primary Efficacy Endpoint(s): Establish group-level daily/weekly baseline normative values for: (1) mean and median number of doses of ProAir® Digihaler™ and AirDuo® Digihaler™, and per-inhalation baseline normative values for (2) peak inspiratory flow (PIF), (3) inspiratory time and (4) volume. We will test the hypothesis that patient-specific baseline usage values are significantly different from usage values collected during or leading up to exacerbation events.
- Secondary Efficacy Endpoint(s): 1. Test the hypothesis that imminent exacerbation events can be predicted using Digihaler™ inhalation parameter measurements. 2. Test the hypothesis that PIF is linearly (or non-linearly) related to FVC and FEV1. Test the hypothesis that there exists a threshold for change in PIF that is associated with a clinically meaningful change (>10%) in lung function. 3. Test the hypothesis that patients with low, moderate, and high adherence to maintenance inhalers have significantly different asthma outcomes. 4. Test the hypothesis that non-responders, partial, and complete responders have significantly different Digihaler™ inhalation parameters. 5. Test the hypothesis that future response to biologics can be predicted using clinical, biological, and digital (inhalation) markers.

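### The PIF–FEV1 analysis in Section 9.4.3 item 2 has no patient term, change variable, unit of pairing or cut-off method, although the objective is surrogacy and a PIF-change threshold

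*Combined protocol and SAP*

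**What the plan says.** The aim is stated in terms of surrogacy and change.

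- Section 3: "To determine whether inhalation measurements can serve as surrogates of standard expiratory flow measurements". The Section 1.1 synopsis adds that the study will "identify thresholds for changes in PIF that are associated with a clinically meaningful increases or decreases (10%) in lung function".
- The Section 3 endpoints for this objective are changes, including "Change in mean peak inspiratory flow (PIF) from baseline up to one year" and "Change in mean forced expiratory volume in one second (FEV1) from baseline up to one year". The tests listed beside them include "Identification of change in PIF thresholds (increase and decrease thresholds) that are clinically meaningful".
- Section 9.1 makes it a hypothesis: "Test the hypothesis that there exists a threshold for change in PIF that is associated with a clinically meaningful change (>10%) in lung function".

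The method is in Section 9.4.3 item 2: scatter plots; Pearson, Kendall and Spearman correlations of pairs; and a plan to "compute univariate linear regression equations with PIF as the predictor", with FEV1 or FVC as the response. A transformation or polynomial term is added if the relation is not linear. The outputs are p-values, coefficients, R-squared and mean absolute error.

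Both measurements are repeated. Section 8.1.2.5 asks for home spirometry on at least "three days per week, at least one of which occurs on the weekend". Under Section 8.1.2.4 the inhaler records inhalation parameters automatically. Participants stay in the study for 12 months (Section 1.1).

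**The concern.** A surrogate for monitoring has to move with FEV1 in the same patient. Patients also differ stably in both measures, through body size, sex, age and fixed airway disease. A correlation across patients can come from those differences alone. Item 2 has nothing that separates the two sources. It also does not say whether a pair is a reading, a day, a patient mean or a change score.

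The study could therefore report a clear, highly significant correlation although PIF tracks nothing within patients, or miss tracking that is real. The threshold hypothesis in Section 9.1 has no stated test at all.

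**Working it through.** **Plan's own PIF figure.** Section 9.2 gives mean 115, SD 15 and 100 patients, with a 95% CI of plus or minus 3. Check: 1.96 × 15/√100 = 2.94. It reproduces, but it concerns mean PIF. The documents give no precision figure for the PIF–FEV1 relation.

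**Inputs.**
- From the documents: 100 patients; at least 3 spirometry days a week. That is 3 × 48 = 144 pairs per patient to the last clinic visit, or 3 × 52 = 156 over a year.
- PIF SD 15 (Section 9.2), taken here as the between-patient SD. The plan does not label it so.
- Assumed: within-patient PIF SD 8; FEV1 SD 0.8 L between and 0.2 L within patients; all correlations.

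**Reading A: repeated readings pooled.**

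Pooled r = (r_b·S_bX·S_bY + r_w·S_wX·S_wY) / √[(S_bX² + S_wX²)(S_bY² + S_wY²)], where b is between and w is within patients.

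Denominator: √[(225 + 64)(0.64 + 0.04)] = √196.52 = 14.02.

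| Between r | Within r | Numerator | Pooled r |
|---|---|---|---|
| 0.5 | 0 | 0.5 × 15 × 0.8 = 6.00 | 0.43 |
| 0 | 0.6 | 0.6 × 8 × 0.2 = 0.96 | 0.07 |
| 0.5 | 0.5 | 6.00 + 0.80 = 6.80 | 0.485 |

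The third row shows that the correlation is little distorted when the two true values happen to be equal.

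*P-values when both true correlations are zero.* The ICCs are 225/289 = 0.779 for PIF and 0.64/0.68 = 0.941 for FEV1. The variance of r is inflated by 1 + (156 − 1) × 0.779 × 0.941 ≈ 114.6, and √114.6 = 10.7. A nominal 5% test then rejects with probability 2 × [1 − Φ(1.96/10.7)] ≈ 0.85. Simulation agrees (about 0.85). The 15,600 pairs carry the information of about 15,600/114.6 = 136 independent ones.

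*Sensitivity.*
- SD 15 as a total SD that already contains the within-patient 8: the between SD is √(225 − 64) = 12.7. Pooled r becomes 0.41 and 0.08 in the first two rows, and the false-positive rate stays about 85%.
- 50 pairs, within-patient SDs 12 and 0.3 L: the denominator is √(369 × 0.73) = 16.41. Pooled r is 6.00/16.41 = 0.37 and 2.16/16.41 = 0.13. The inflation is 1 + 49 × 0.610 × 0.877 = 27.2, giving a false-positive rate of about 71%.
- Common ICC of 0.5 to 0.9 for both measures: false-positive rate 58% to 75% at 48 pairs, and 75% to 86% at 144.

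*Can a threshold be read off the pooled slope?* The pooled slope is the numerator divided by 289. In the second row it is 0.96/289 = 0.0033 L per PIF unit, against a within-patient slope of 0.6 × 0.2/8 = 0.015. Inverting the pooled slope overstates the PIF change needed by a factor of 289/64 = 4.5. In the first row the pooled slope is 6/289 = 0.021 while the within-patient slope is zero, so a threshold would be computed where none exists. Even in the third row it is 6.8/289 = 0.024 against 0.5 × 0.2/8 = 0.0125.

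**Reading B: one mean per patient.** The points are independent and the p-values valid. But the correlation then estimates the between-patient relation only. In simulations with between r 0.6 and within r 0 it averaged 0.59 to 0.60. It says nothing about change.

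**Within-patient analysis of repeated readings.** With each patient's readings centred on that patient's mean (100 patients, 48 pairs, ICC 0.5 to 0.9), true within-patient correlations of 0 and 0.6 were recovered as 0.00 and 0.60. The 5% test rejected in 3% to 5% of runs when the true value was zero.

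**The case against.** The best defence is that Section 3 shows a change analysis was intended. The endpoints there are changes from baseline, and the correlations, regressions and thresholds are listed beside them. If item 2 were run on one change score per patient, the question would be on the right scale and the points independent. This stands as evidence of intent. But item 2 does not mention change, and neither place says how a cut-off for a 10% FEV1 change would be found. The confusion matrix in Section 3 sets PIF change against exacerbations and poor control, not against FEV1. The exploratory list in Section 9.4.9 names time series and multivariable methods in general terms only.

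A reader might infer that the plan commits to treating thousands of readings as independent. The documents do not say so. Pooling is the natural reading of a univariate regression on repeated data, but it remains an inference, and the figures under Reading A depend on it. A reader might also infer that the published confidence intervals would be badly wrong. Item 2 promises p-values but no interval, so the false-positive rate is the relevant measure.

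The 156 pairs are not a maximum, since more readings are encouraged. Nor are they a minimum: Sections 6.4 and 7.1 let a patient keep only one digital inhaler, possibly the as-needed one, so a spirometry day may have no PIF.

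**Conclusion.** The point holds as a mismatch between aim and written method. Item 2 cannot answer the within-patient question under pooling or under patient means, and no section gives a way to derive the threshold that Sections 1.1, 3 and 9.1 promise.

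The size is conditional. If readings are pooled, and under the SDs above, the correlation can be 0.43 with no within-patient relation or 0.07 with a strong one, and false-positive rates are about 58% to 86% over the settings tried. The exact values rest on assumed SDs and correlations. The mechanism does not, although the correlation itself is little distorted if the between- and within-patient values are equal.

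It would go too far to say that the data cannot answer the question: the planned readings can support a within-patient analysis. It would also go too far to treat this as a threat to the whole study. The primary objective and the sample size do not depend on it. It should be fixed before analysis.

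**What to change.** Amend Section 9.4.3 item 2 as follows.

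1. State the pairing rule: which device's inhalations count, the time window that links them to a spirometry session, and how several inhalations in the window are summarised.
2. Make the main analysis a mixed model of FEV1 (and, separately, FVC) on PIF centred on the patient's mean, plus that mean, with a random patient intercept. An equivalent repeated-measures method would also serve. Report the within-patient slope and correlation, with inference at patient level (for example a cluster bootstrap).
3. Derive the threshold from within-patient change in PIF against a 10% within-patient change in FEV1, separately for increases and decreases. Define the reference period for change. An ROC analysis that resamples patients is one suitable method.
4. Keep pooled scatter plots and correlations as description, without p-values.

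The cost is wording and a little more analysis in standard software, with no new data. Intervals will be wider than a pooled analysis would suggest, because they reflect about 100 patients and not thousands of independent readings.
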